4. LIST OF ABBREVIATIONS

ΔHSDS	change in height standard deviation score
μg	microgram
ACP-001	TransCon PEG80 hGH
ACP-011	TransCon PEG40 hGH
ADHD	attention-deficit/hyperactivity disorder
AE	adverse event
AGHD	adult growth hormone deficiency
AUC	area under the curve
BIH	benign intracranial hypertension
C&OS	Convenience & Overall Satisfaction domains of the abbreviated Treatment Satisfaction Questionnaire for Medication v9
C&OS-P	Convenience & Overall Satisfaction domains of the abbreviated Treatment Satisfaction Questionnaire for Medication v9 – Parent
CFR	Code of Federal Regulations
cm	centimeter
C _{max}	maximum observed concentration
CSDS	Child Sheehan Disability Scale
CSDS-C	Child Sheehan Disability Scale – Child
CSDS-P	Child Sheehan Disability Scale – Parent
CRO	Contract Research Organization
CV	completion visit
d	day
DCC	dual chamber cartridge
DMP	data management plan
DUQ	Device Usability Questionnaire
eCRF	electronic case report form
ETV	early termination visit
FDA	Food and Drug Administration
FT3	Free triiodothyronine
FT4	Free thyroxine
GCP	Good Clinical Practice
GH	growth hormone
GHD	growth hormone deficiency
GHRH	growth hormone-releasing hormone
GLP	Good Laboratory Practice
hCG	human chorionic gonadotropin
HbA1c	hemoglobin A1c
hGH	human growth hormone
HREC	Human Research Ethics Committee

HV	height velocity
ICH	International Council on Harmonization
ICF	informed consent form
IEC	Independent Ethics Committee
IGF-1	insulin-like growth factor-1
IGFBP-3	insulin-like growth factor binding protein-3
IM	investigator meeting
IRB	Institutional Review Board
ISC	Independent Safety Committee
IWRS	interactive web response system
kDa	kilodalton
kg	kilogram
MedDRA	Medical Dictionary for Regulatory Activities
mg	milligram
mL	milliliter
mPEG	methoxypolyethylene glycol
MPH	mid-parental height
ng	nanogram
PD	pharmacodynamics
PEG	polyethylene glycol
pH	power of hydrogen
PK	pharmacokinetics
PQ	Preference Questionnaire
PQ-C	Preference Questionnaire – Child
PQ-P	Preference Questionnaire – Parent
SAE	serious adverse event
SAP	statistical analysis plan
SC	subcutaneous
SD	standard deviation
SDS	standard deviation score
SIV	site initiation visit
SOP	standard operating procedures
SUSAR	suspected unexpected serious adverse reaction
sWFI	sterile water for injection
TSQM	Treatment Satisfaction Questionnaire for Medication
TSQM-9	Abbreviated Treatment Satisfaction Questionnaire for Medication v9
TSH	thyroid stimulating hormone
WHO	World Health Organization

5. INTRODUCTION

5.1. BACKGROUND AND RATIONALE

hGH is a product of endocrine secretion of the pituitary gland, which targets tissues to promote growth in children and control metabolism in children and adults. It is secreted by somatotroph cells located in the lateral wings of the anterior pituitary gland. The most important and obvious function of hGH is growth promotion of children. Through its IGF-1 mediated effects (as well as less obvious direct effects), it stimulates cartilage and bone growth by enhancing the activity of chondroblasts and osteoblasts and promoting collagen synthesis. In addition, hGH has important metabolic functions: it exerts potent anti-insulin effects resulting in decreased glucose utilization (and resultant increased plasma glucose levels) and increased lipolysis (in contrast to the opposing actions of IGF-1 to lower plasma glucose and increase lipogenesis); these functions underlie its continued secretion into adulthood. New research continues to reveal other potential roles of hGH, including regulation of cardiac and immune function, mental agility and aging.

GHD is the result of impaired production or secretion of hGH, which can appear at any time point in life and is due to various known and unknown factors. The etiology of childhood GHD is most commonly of hypothalamic origin with impaired GHRH secretion, the most common diagnosis being isolated idiopathic GHD. GHD is a well-recognized clinical entity in adults as well. It causes abnormalities in body composition, lipid metabolism, and physical and psychosocial function, all of which improve with hGH replacement therapy.

At the present time, however, there are no commercially available sustained-release or long-acting hGH preparations. Currently hGH is available only as daily injection formulations, thus causing a significant burden and interruption of normal daily life to children and their parents, as well as compliance issues. Decreased compliance with daily hGH therapy is known to result in sub-optimal height outcomes (*Cutfield, 2011*). If a weekly long-acting hGH product were to have similar efficacy, safety, and tolerability while maintaining hGH exposure in the optimal therapeutic range as existing daily therapies, preference and satisfaction for the weekly regimen would likely exist, with improved compliance to follow.

TransCon hGH is a weekly administered hGH prodrug that liberates unmodified hGH as the active pharmaceutical ingredient through controlled auto-hydrolysis resulting in sustained release of hGH. TransCon hGH consists of hGH that is transiently conjugated to mPEG via a (TransCon) linker.

The linker that forms the bridge between the protein and mPEG moieties is stable at pH 5.0. However, after introduction into a physiological pH and temperature (ie, after injection of TransCon hGH), autohydrolysis of the linker occurs in a controlled manner that follows first-order kinetics, whereby unmodified, fully-active hGH is released. As the released hGH is completely unmodified, it is expected to have the same mode of action and tissue distribution as endogenous hGH. This is important for optimal efficacy, as a portion of hGH activity is mediated by local hGH effects in target tissue, including the growth plate and adipocytes. The release of hGH also liberates N1, -N1, -N3-trimethyl-1,3-propane-diamine, a small molecular weight compound associated with the linker. The remainder of the inactive mPEG-linker component of TransCon hGH is cleared from the body through natural mechanisms for other high molecular weight molecules.

The exposure-toxicity relationship of PEG in animals and humans has been well investigated and metabolism/excretion of PEG is well understood, indicating that the PEG associated with a biological molecule represents an acceptable benefit-risk ratio to humans (*Webster, 2007*). Detailed information is provided in the Investigator's Brochure.

The Sponsor initiated the TransCon hGH development program with TransCon hGH (ACP-001), in which the carrier was 80 kDa mPEG, and for which four clinical trials were conducted: two phase 1 trials in healthy adults, one phase 2 trial in adult GHD, and one 6-month phase 2 trial in pediatric GHD. Upon completion of the TransCon hGH (ACP-001) phase 2 clinical program, the Sponsor modified the TransCon hGH product by replacing the 80 kDa mPEG with a 40 kDa mPEG, with the understanding that this difference in mPEG would not significantly affect the autohydrolytic release of hGH, the prolonged half-life, or the inactive nature of the parent TransCon hGH product. The linker component and hGH remained the same between TransCon hGH (ACP-001) and TransCon hGH (ACP-011); the only change was the reduction in mPEG carrier size. This change resulted in TransCon hGH (ACP-011), a drug product that is functionally equivalent in PK, PD, and safety/tolerability to its predecessor, but with lower viscosity and higher product concentration that enables smaller injection volumes and the use of a small-gauge needle. Additionally, the PEG exposure was reduced by $\geq 50\%$.

5.2. RELEVANT FINDINGS FROM NONCLINICAL STUDIES

Nonclinical pharmacology and toxicology studies have been conducted to support the clinical development program involving weekly SC administration of TransCon hGH (ACP-011) in children with growth hormone deficiency. All pivotal nonclinical safety studies either have been or are being conducted in compliance with Good Laboratory Practices (GLP) and the program as a whole follows recommendations provided by ICH guidance and product specific guidance from health authorities. The nonclinical program has assessed both the parent prodrug and the products of autohydrolysis (hGH, the remainder mPEG-linker [measured as mPEG40], and TMPD) as well as IGF-1, the PD biomarker for hGH.

Please refer to the current Investigator's Brochure for detailed information pertaining to the nonclinical program supporting conduct of this clinical trial.

5.3. CLINICAL EXPERIENCE

A phase 1 clinical trial of TransCon hGH (ACP-001) in healthy male volunteers has been conducted as a randomized, double-blind, dose-escalation trial versus placebo and daily hGH (Omnitrope) investigating the safety, tolerability, pharmacokinetics (PK) and pharmacodynamics (PD) response in 44 healthy male subjects. No negative effects of the test drug were detected when compared to placebo and the active comparator (Omnitrope). The test product was well tolerated at up to 0.24 mg hGH/kg when injected once subcutaneously to 28 healthy male subjects.

[figure not shown]
A second phase 1 single-dose trial investigated the safety and tolerability of TransCon hGH (ACP-001) at 2 different dose-levels, 0.30 mg hGH/kg and 0.36 mg hGH/kg, respectively, in 24 male and female healthy subjects. ACP-001 was well tolerated with no safety concerns.

A phase 2 clinical trial in adult subjects with GHD was a randomized, open-label, active-controlled trial of 3 dose levels of TransCon hGH (ACP-001) (0.02, 0.04 and 0.08 mg

hGH/kg/week) compared to daily hGH (Omnitrope 0.04 mg hGH/kg/week divided into 7 equal daily doses) over 4 weeks. A total of 37 subjects were randomized. ACP-001 was well tolerated with no safety concerns. Detailed information is given in the Investigator’s Brochure.

A phase 2 clinical trial in pediatric subjects with GHD has been conducted as a multicenter, randomized, open-label, active-controlled, parallel-group trial of 3 doses of TransCon hGH (ACP-001; 0.14, 0.21 and 0.30 mg hGH/kg/week) compared to daily hGH (Genotropin 0.21 mg hGH/kg/week divided into 7 equal daily doses) over 26 weeks. 55 subjects were randomized, of whom 53 received investigational product (12 subjects in the 0.14 mg hGH/kg/week, 14 subjects in the 0.21 mg hGH/kg/week and 14 subjects in the 0.30 mg hGH/kg/week TransCon hGH cohorts and 13 subjects in the 0.21 mg hGH/kg/week Genotropin cohort). Mean annualized HV among the 3 dose levels administered weekly ranged from 11.9 cm for the 0.14 mg/kg/week dose to 12.9 cm for the 0.21 mg hGH/kg/week dose to 13.9 cm for the 0.30 mg hGH/kg/week dose, which were all comparable to 11.6 cm for the active comparator, daily injections of Genotropin at a 0.21 mg hGH/kg/week dose (Figure 1).

Figure 1: Annualized Height Velocity (Mean +SD) in 53 Subjects After 26 Weeks of TransCon hGH vs. Genotropin Treatment

cm = centimeter; kg = kilogram; mg = milligram

No reports of drug-related serious or unexpected AEs were observed. AEs were generally mild and observed at the same level and nature compared between the 3 TransCon hGH cohorts and the Genotropin cohort. Injection site reactions were generally mild and transient and were observed at a rate that was similar to the daily hGH control arm. There were no observations of injection site nodule formation or lipoatrophy. Low immunogenicity (a single subject with a low titer) was consistent with published data for daily hGH. No neutralizing antibodies were

detected. Maximum and average hGH blood concentration were comparable between equivalent weekly doses of TransCon hGH and daily hGH.

The clinical safety profile of ACP-001 was overall comparable to daily hGH. Headache and fatigue were the most frequent drug-related AEs during the phase 2 adult growth hormone deficiency (AGHD) trial and were reported in all treatment groups. No AEs were judged to be definitely drug-related.

TransCon hGH (ACP-011) was found to be bioequivalent (with comparable PK, PD, safety and tolerability) in a Phase 1 single center, randomized, open-label trial to evaluate comparability of PK and PD parameters of ACP-001 and ACP-011.

In a trial completed in 2018, TransCon hGH (ACP-011) administered by two modalities (syringe/needle versus GH Auto-Injector) was confirmed to be bioequivalent (with comparable PK, PD, safety and tolerability) in a phase 1, randomized, open-label, single-dose, crossover study in healthy adult males.

A global phase 3 trial, called the TransCon hGH CT-301 (heiGHt) trial in children with GHD, was initiated in September 2016 and is ongoing. The heiGHt trial is a randomized, open-label, active-controlled phase 3 registration trial that is designed to enroll approximately 150 children with GHD who have not previously been treated. The inclusion criteria require subjects to be pre-pubertal children with bone age that is at least six months less than chronological age, impaired height that is either greater than or equal to two standard deviations (SD) below the population mean or at least 1.5 SD below mid-parental height (MPH), GHD diagnosis confirmed by two different GH stimulation tests, and IGF-1 that is greater than or equal to one SD below the population mean. Subjects will receive either once-weekly TransCon hGH (0.24 mg hGH/kg/week) or daily injections of Genotropin at 34 µg/kg/day (0.24 mg hGH/kg/week) with a 2:1 randomization in a non-inferiority design. The primary endpoint of the trial is height velocity after 52 weeks of treatment. Other key endpoints include an annualized HV at earlier time points, change in height standard deviation scores over 52 weeks, normalization of IGF-1 SDS, change in serum IGF-1 and IGFBP-3 levels, and change in IGF-1 and IGFBP-3 SDS.

A second phase 3 trial called the TransCon hGH CT-302 (fliGHt) trial in children with GHD was initiated in 2017. Approximately 150 subjects (ages 3 to 17 years old) enrolled in fliGHt will have been treated previously with commercial hGH (from 13 weeks to 130 weeks) and will switch to TransCon hGH. In addition, children with GHD who are 6 months to < 3 years old may or may not have been previously treated with commercial hGH. The treatment period in fliGHt is 6 months. The primary outcome is safety and tolerability.

5.4. TRIAL RATIONALE

In comparison to the heiGHt and fliGHt trials, the primary objective of this extension trial is to assess the long-term safety of weekly TransCon hGH (ACP-011) in children with GHD previously treated in a TransCon hGH trial. Additionally, when the GH Auto-Injector, a unique device developed specifically for the administration of TransCon hGH, becomes available, subjects will be switched from the administration of TransCon hGH by syringe and needle to the GH Auto-Injector in the US only.

Preference and satisfaction for dosing with TransCon hGH or Genotropin will also be evaluated.

5.5. SUMMARY OF POTENTIAL RISKS AND BENEFITS

TransCon hGH (ACP-011) is an investigational medicinal hGH prodrug product with a proposed once-weekly dosing regimen designed to overcome the inconvenience and suboptimal compliance of daily hGH injections. The safety and efficacy profile is anticipated to be comparable to currently approved daily hGH products, while maintaining exposure (C_{max} and AUC) in the optimal therapeutic range. Moreover, the biodistribution is designed to be the same as with established daily hGH products. Obviating the need for daily injections should increase compliance and therefore long-term efficacy, which would be of great benefit to pediatric patients with GHD (*European Union, 2008*).

TransCon hGH administered by the GH Auto-Injector is expected to have a comparable safety profile to TransCon hGH administered by syringe and needle as well as to daily hGH formulations.

6. OBJECTIVES

6.1. PRIMARY OBJECTIVE

To assess long-term safety of weekly TransCon hGH in children with GHD previously treated in a phase 3 TransCon hGH trial

6.2. SECONDARY OBJECTIVES

- To assess annualized HV with long-term dosing of weekly TransCon hGH treatment
- To assess the proportion of subjects with IGF-1 SDS in the normal range of 0.0 to +2.0 with long-term dosing of weekly TransCon hGH treatment
- To evaluate the Δ HSDS with long-term dosing of weekly TransCon hGH treatment
- To determine the incidence of antibodies against TransCon hGH (anti-hGH and anti-PEG) with long-term dosing of weekly TransCon hGH treatment
- To assess the preference for weekly TransCon hGH or daily Genotropin
- To assess the treatment satisfaction of weekly TransCon hGH over time
- In subjects using the GH Auto-Injector: to assess comfort, ease-of-use, and safety

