7. Pubertal status assessment (Tanner stage)
8. Blood collection for the following laboratory assessments*:
 - IGF-1 and IGFBP-3
 - Antibodies against hGH and PEG
 - If warranted, TransCon hGH, hGH, and PEG serum levels may be analyzed for the interpretation of immunogenicity titers
 - mPEG

- Hormone/glycemic Status (TSH, FT4, FT3, morning cortisol, and HbA1c)
- Chemistry
- Hematology
- Lipid panel
- **Females of child-bearing potential only:** hCG
*Fasting not required. Banked blood samples may be used for additional characterization of anti-drug antibody responses.

9. Investigational product dose adjustment, as needed

10. Investigational product & subject diary dispensing

An overview of all visits is provided in the Schedule of Events, Section 18.2.

10.2.2.4. Patient-Reported Outcome Completion (6th week after transition to the GH Auto-Injector) and Device Usability Questionnaire

For all subjects who have transitioned to the GH Auto-Injector (6th week of GH Auto-Injector Use): Immediately prior to the 6th dose of the GH Auto-Injector, and at the next scheduled clinic visit (approximately 13 weeks after transition to the GH Auto-Injector), patient-reported outcomes questionnaires will be completed by subjects/parents/legal guardians/caregivers, as applicable. At 6 weeks after transition to the GH Auto-Injector, the questionnaires will be completed in the subject diary. At the next scheduled clinic visit (approximately 13 weeks after transition to the GH Auto-Injector), the questionnaires will be completed at the clinic visit, prior to review of the subject diary, AEs, and concomitant medications. The questionnaires are:

- C&OS-P
- CSDS-P
- **CSDS-C: only for subjects ≥ 9 years old (at time of transition to GH Auto-Injector)**

In addition, on the day of the 6th dose using the GH Auto-Injector (either immediately before or after the 6th dose) and at the next scheduled clinic visit (approximately 13 weeks after transition to GH Auto-Injector), the following questionnaire will be completed by the individual primarily responsible for preparing and performing the injection with the GH Auto-Injector.

- DUQ

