- ³ Medications and health status: Interval history only to be recorded in case of new disease states since the last visit of the prior trial; disease states diagnosed since the initiation of the prior trial (eg, new onset migraines) are medical history; Medical history from the prior trial will be carried forward into this trial's database; Ongoing AEs from the prior trial will be followed until resolution or stabilization; Review of subject diary from the prior trial; Current therapies.
- ⁴ Vital sign measurements include heart rate, blood pressure, respiratory rate and body temperature, which should be performed after the subject has rested for at least 5 minutes.
- ⁵ Height should be measured at each visit at approximately the same time of day, preferably by the same auxologist.
- ⁶ Blood sample collection – A includes IGF-1, IGFBP-3, antibodies against hGH and PEG, and for females of child-bearing potential hCG. If warranted, TransCon hGH, hGH, and PEG serum levels may be analyzed for the interpretation of immunogenicity titers
- ⁷ Blood sample collection – B includes mPEG, hormone/glycemic status (TSH, FT4, FT3, morning cortisol, and HbA1c), chemistry, hematology, and lipid panel. Fasting not required.
- ⁸ Bone age x-ray may not be required at Visit 1 if there is documentation of a bone age x-ray performed within the past 52 weeks. However, if subject's prior documented bone age was > 12.0 years, and it was performed greater than 9 months prior to Visit 1, a bone age x-ray should be performed within approximately 4 weeks of Visit 1. Bone age x-ray may also be performed at any time, if clinically indicated.
- ⁹ Once the GH Auto-Injector is available, transition to the GH Auto-Injector will occur in the US (only) at the next regularly scheduled trial visit when thorough training on preparation and administration will occur.
- ¹⁰ At Visit 1, the C&OS-P, CSDS-P, and CSDS-C should be completed for all subjects.

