- ¹¹ For subjects who were treated with Genotropin in the prior TransCon hGH CT-301 trial, C&OS-P, CSDS-P, CSDS-C, PQ-P, and PQ-C will be completed (as applicable) within the subject diary immediately prior to the 6th dose of investigational product, and in clinic at Visit 2, prior to review of the subject diary, AEs, and concomitant medications. For subjects transitioning to the GH Auto-Injector, C&OS-P, CSDS-P, and CSDS-C will be completed (as applicable) within the subject diary immediately prior to the 6th dose after transition to the GH Auto-Injector, and again in clinic at the following scheduled visit, prior to review of the subject diary, AEs, and concomitant medications. Additionally, for subjects transitioning to the GH Auto-Injector, the DUQ will be completed within the subject diary on the day of the 6th dose of investigational product, and in clinic at Visit 2, prior to review of the subject diary, AEs, and concomitant medications.
- ¹² CSDS-C and PQ-C should only be completed by subjects \geq 9 years old at the time of Visit 1, and/or at the transition to the GH Auto-Injector, as applicable.
- ¹³ Dose adjustments at visits are typically based on subject weight at visits. However, dose adjustments may occur between visits per Section 9.6.
- ¹⁴ Local tolerability assessment at the injection site to be performed at time of injection, and by the trial staff at visits.
- ¹⁵ Investigational product compliance includes review of subject diary and returned investigational product.
- ¹⁶ AE review includes review of subject diary and physical examination of injection sites. AEs that are considered mild and not related to investigational product will not be reported on the AE CRF. AEs reported up to 14 days after the final dose of TransCon hGH will be captured.

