Instructions: Please take some time to think about your level of satisfaction or dissatisfaction with the medication your child is taking in this clinical trial. We are interested in your evaluation of the convenience of the medication and your overall satisfaction with the medication over the last two to three weeks or since your child last used it.	
For each question, please place a single check mark next to the response that most closely corresponds to your own experiences.	
1. How easy or difficult is it to use the medication in its current form?	
 ₁ Extremely Difficult	
 ₂ Very Difficult	
 ₃ Difficult	
 ₄ Somewhat Easy	
 ₅ Easy	
 ₆ Very Easy	
 ₇ Extremely Easy	
2. How easy or difficult is it to plan when your child will use the medication each time?	
 ₁ Extremely Difficult	
 ₂ Very Difficult	
 ₃ Difficult	
 ₄ Somewhat Easy	
 ₅ Easy	
 ₆ Very Easy	
 ₇ Extremely Easy	
3. How convenient or inconvenient is it to take the medication as instructed?	
 ₁ Extremely Inconvenient	
 ₂ Very Inconvenient	
 ₃ Inconvenient	
 ₄ Somewhat Convenient	
 ₅ Convenient	
 ₆ Very Convenient	
 ₇ Extremely Convenient	

enliGHten Visit ____

ID #

C&OS-PARENT (Continued)

4. Overall, how confident are you that taking this medication is a good thing for your child?

- ₁ Not at All Confident
- ₂ A Little Confident
- ₃ Somewhat Confident
- ₄ Very Confident
- ₅ Extremely Confident

5. How certain are you that the good things about your child's medication outweigh the bad things?

- ₁ Not at All Certain
- ₂ A Little Certain
- ₃ Somewhat Certain
- ₄ Very Certain
- ₅ Extremely Certain

6. Taking all things into account, how satisfied or dissatisfied are you with this medication?

- ₁ Extremely Dissatisfied
- ₂ Very Dissatisfied
- ₃ Dissatisfied
- ₄ Somewhat Satisfied
- ₅ Satisfied
- ₆ Very Satisfied
- ₇ Extremely Satisfied

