11.2. Child Sheehan Disability Scale

The CSDS is an adaptation of the Sheehan Disability Scale to assess impairment related to childhood anxiety on children and their parents. This measure is being adapted in this trial to assess impairment related to treatment burden on children and their parents/legal guardians/caregivers.

At Visit 1 for all subjects, the parent/legal guardian/caregiver will complete the CSDS-P, while the subject, if \geq 9 years old, will complete the CSDS-C.

Summary score will be the sum of each question score at each visit. It will be calculated based on child and parent separately.

Each question for CSDS-P and CSDS-C at each time point will be summarized. Listings will also be provided for CSDS-P and CSDS-C.

11.3. Convenience & Overall Satisfaction Domains of the Treatment Satisfaction Questionnaire for Medication

At Visit 1, the Convenience and Overall Satisfaction (C&OS) of the Treatment Satisfaction Questionnaire for Medication (TSQM-9) is administered to all subjects.

Only the parent/legal guardian/caregiver will complete the C&OS of the TSQM-9, thus it has been identified for this trial as the C&OS – Parent (C&OS-P).

The study C&OS-P contains two sections including convenience section (item 1-3) and global satisfaction section (item 4-6) on the questionnaires. In order to derive a summary score, the following rules are used.

The convenience score will be set as follows:

- (1) $100 * (\text{sum}(\text{item 1 to 3}) - 3) / 18$, if all the items are presented;
- (2) $100 * (\text{sum}(\text{two items}) - 2) / 12$, if one item is missing,
- (3) Missing if more than one item is missing;

The global satisfaction score will be set as follows:

- (1) $100 * (\text{sum}(\text{item 4 to 6}) - 3) / 14$, if all the items are presented;
- (2) $100 * (\text{sum}(\text{two items}) - 2) / 10$ if item 4 or 5 is missing
- (3) $100 * (\text{sum}(\text{item 4 and 5}) - 2) / 8$ if item 6 is missing
- (4) Missing if more than one more item is missing

Each question for C&OS -P, and the summary score, i.e., convenience score and global satisfaction score, will be summarized at each time point by each group and overall. Listings will also be provided for C&OS -P as well.

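### Satisfaction with weekly TransCon hGH over time rests on ratings about 7 weeks apart or across a device change, and subjects already on TransCon who keep their device give one extension rating

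*Protocol*

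**What the plan says.** Protocol 6.2 sets the objective "To assess the treatment satisfaction of weekly TransCon hGH over time". The matching endpoint in Protocol 14.1.4 is satisfaction with weekly TransCon hGH, listed under other endpoints. Protocol 11.7.3 makes the six-item C&OS-P the satisfaction measure.

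The form is scheduled by three routes:

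- Everyone, once (Protocol 18.2, note 10): "At Visit 1, the C&OS-P, CSDS-P, and CSDS-C should be completed for all subjects".
- Former Genotropin subjects only, before the 6th dose and at Visit 2 (Protocol 10.2.2.1; 18.2, note 11): "For subjects who were treated with Genotropin in the prior TransCon hGH CT-301 trial, C&OS-P, CSDS-P, CSDS-C, PQ-P, and PQ-C will be completed".
- Auto-injector switchers only, before the 6th device dose and at the next clinic visit, about 13 weeks after transition (Protocol 10.2.2.4). This route is confined to one country, since "transition to the GH Auto-Injector will occur in the US (only) at the next regularly scheduled trial visit" (18.2, note 9).

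The Schedule of Events has no C&OS-P at Visits 3, 4 or 5. The lists for later even- and odd-numbered visits (10.2.2.2 and 10.2.2.3) contain no questionnaire. The completion/early termination visit takes its procedures from Visit 5 (10.2.4). Treatment is open-ended, with visits every 13 weeks (7.1.1).

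The form asks about "your overall satisfaction with the medication over the last two to three weeks" (Protocol Appendix 5). SAP 11.3 states that the items and the two summary scores "will be summarized at each time point by each group and overall".

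**The concern.** A statement about satisfaction over time needs repeated ratings of the same treatment in the same families. Most of the schedule does not supply them. A child already on TransCon at entry who never changes device is rated once, at Visit 1. For a former Genotropin child, the short recall period means that the Visit 1 form rates daily Genotropin. For a child who moves to the auto-injector, the later ratings follow a new device, so time on drug and change of device cannot be separated.

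Protocol 5.1 expects satisfaction with the weekly regimen to lead to better compliance, so whether satisfaction lasts is of interest in a trial with indefinite dosing. The schedule cannot show that for the trial population, and no satisfaction rating is scheduled when a family leaves. There is also a reading problem. An overall column printed visit by visit looks like a trend, but the children and, in part, the drug differ between its entries.

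**Working it through.** **Inputs.** CT-301: about 150 children, randomised 2:1 to TransCon or Genotropin (Protocol 5.3). CT-302: about 150 (Protocol 5.3). Planned extension size: up to about 300 (Protocol 8). SAP 3.2 gives about 400, but that SAP cites Protocol 1.0. Full rollover is assumed. The fraction *u* of non-Genotropin subjects who move to the auto-injector is not in the documents and is varied.

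**Planned size.** 150 + 150 = 300, which agrees with the protocol. The same inputs do not give 400.

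**Former Genotropin subjects.** 150 × 1/3 = 50, or 50/300 = 16.7%. The other 250 are CT-301 TransCon (100) and CT-302 (150).

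**Share with a Visit 1 rating only** = (1 − u)(N − 50)/N.

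| u | N = 300 | N = 400 |
|---|---|---|
| 0 | 250/300 = 83.3% | 350/400 = 87.5% |
| 0.2 | 200/300 = 66.7% | 280/400 = 70.0% |
| 0.3 | 175/300 = 58.3% | 245/400 = 61.3% |
| 0.4 | 150/300 = 50.0% | 210/400 = 52.5% |
| 1 | 0% | 0% |

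The share falls to one half at u = (150 − 50)/250 = 0.40 for N = 300, and at u = (200 − 50)/350 = 0.43 for N = 400.

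**Longest interval between TransCon ratings on one device.** By group:

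- CT-301 TransCon or CT-302, no switch: one rating, so no interval.
- Former Genotropin, no switch: Week 6 and Week 13, which is 13 − 6 = 7 weeks (11 − 6 = 5 to 15 − 6 = 9 with the Visit 2 window).
- CT-301 TransCon or CT-302, switching: Visit 1 before the device, then the 6th device dose and the next visit. The two device ratings are again about 7 weeks apart; the longer interval back to Visit 1 crosses the change of device.
- Former Genotropin, switching at Visit 2 or later: up to four TransCon ratings, namely Weeks 6 and 13 on syringe and two on the device. Each pair is about 7 weeks apart, and the longer span crosses the change of device.

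**Composition of the overall column in SAP 11.3.** At Visit 1 it holds about 300 ratings: 50 of daily Genotropin (50/300 = 17%) and 250 of TransCon. At Visit 2 it holds the 50 former Genotropin subjects plus any recent switchers. With no switching, none of the 250 children who rated TransCon at Visit 1 appears at Visit 2, and all 50 who do appear had rated another drug at Visit 1. SAP Table 2 has no Week 6 row and no axis for time since transition, so the diary forms and post-switch forms have no defined time point in the analysis windows.

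**The case against.** The strongest case for the plan has several parts.

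- The height velocity, IGF-1, height SDS and antibody objectives all refer to long-term dosing; the satisfaction objective does not. Its endpoint is descriptive and sits under other endpoints in a trial whose primary objective is safety. This is correct, and it limits the severity. Even so, describing satisfaction over time takes at least two ratings per subject, and non-switchers already on TransCon have one.
- A reader might infer that the questionnaire stops about 13 weeks after entry for everyone, or that the objective cannot be answered at all. The documents do not support either reading. The switchers' clock starts at transition, which may fall long after entry. A rating exists at the transition visit if that is Visit 1, or Visit 2 for a former Genotropin subject. A CT-301 TransCon child's Visit 1 rating follows a 52-week trial, so a later device rating is a long-interval repeat, though confounded with device.
- A reader might also infer that most subjects are never asked again. That depends on an unstated switching fraction; 83% is a ceiling.
- SAP 11.3 plans no change score or test for C&OS-P, and it reports each parent-treatment group separately. The introduction to SAP 11 names satisfaction with daily hGH among the data collected, so the Genotropin rating at Visit 1 is intended. The by-group columns limit the pooling problem but leave the overall column as it is.
- Reasons for discontinuation are recorded (Protocol 8.2) and summarised (SAP 6.1), so dissatisfied leavers are not wholly unseen. They still give no exit C&OS-P.
- C&OS-P ratings from the parent trials may exist. The documents do not describe them, and they would add nothing after entry to the extension.

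**Conclusion.** The point holds in a limited form. Satisfaction with weekly TransCon hGH over time can be described over about 7 weeks in former Genotropin subjects and across a change of device in US switchers, but not long-term on one device in the trial population. The share of subjects with a single extension rating is 83% with no switching and 67%, 58% or 50% if 20%, 30% or 40% of the non-Genotropin subjects switch. This assumes about 300 enrolled, full rollover and the 2:1 split. The schedule facts and the 7-week limit do not depend on those assumptions. The overall column of SAP 11.3 should not be read across time points, because about 17% of its Visit 1 ratings concern another drug and its Visit 2 entry comes largely or wholly from former Genotropin subjects unless many subjects switch early. The sponsor should correct this, but it bears on a descriptive secondary objective and leaves the safety objective untouched.

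**What to change.** 1. **Protocol 10.2.2 and 18.2.** Schedule C&OS-P for all parents at Visit 5 and each later annual visit, at the completion/early termination visit, and at the auto-injector transition visit before first device use where no form is already due. The cost is a protocol amendment and a few minutes per family per year, using an existing six-item form at visits already planned. If the sponsor declines new collection, it should narrow the objective in 6.2 to the groups and periods actually measured. In the same amendment, correct 11.7.3, which points to 10.2.2.2 for timing, although that section lists no questionnaire and the device timing is in 10.2.2.4.
2. **SAP 11.3.** Label the Genotropin group's Visit 1 score as a daily-Genotropin rating and leave it out of the overall TransCon column. Present change over time only in subjects with paired TransCon ratings. Index post-switch values by time since transition. This costs a SAP revision and some programming, and needs no new data.
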